Use of an Unapproved Drug or Biologic, or if use of this drug or biologic requires an IND:	
Identify all persons who will prescribe the drug or biologic:	The study doctor and PI, [name]. will prescribe the drug.
The route of administration:	Oral
"Other" route, specify:	No Value Entered
The location(s) where the drug/biologic will be administered:	[name] Study Participant's Residence
If you indicated that administration will take place in an inpatient unit, or at a non-	No Value Entered

Generic name of the drug/biologic

Investigational Drug/Biologics Information

UCLA site, specify the location and where in the location the medication will be administered:

View Memantine

The trade name of the Drug/Biologic:	Namenda					
Indicate the manufacturer:	UCLA pharmacy					
Indicate the source of the study drug/biologic:	UCLA Pharmacy					
If you indicated "Other" and/or that the study drug/biologic is being provided by a pharmaceutical company other than the sponsor, identify the source:	No Value Entered					
Attach the Investigator's Brochure (IB) or package insert	
 
 Document Name	namenda_pi.pdf	
 
 Document Version #	0.01	
 
		Document Name	namenda_pi.pdf	Document Version #	0.01
Document Name	namenda_pi.pdf					
Document Version #	0.01					
Indicate the regulatory status of the drug or biologic:	Investigational Use of a Marketed Drug or Biologic: The drug/biologic will be used off-label for an indication not in the approved labeling.					
Investigational Use of a Marketed Drug or Biologic:	
 
 Describe the approved indications for the use of the drug/biologic and how the drug/biologic will be used in the study:	 
Approved indications and usage: Namenda (memantine hydrochloride) is indicated for the treatment of moderate to severe dementia of the Alzheimer's type. Patients who meet all eligibility criteria at baseline will be given a 14-day supply of the study medications prepared and dispensed by the UCLA Pharmacy in the matching capsules. All subjects will receive 10-20mg of escitalopram open-label throughout the trial. Matching capsules containing memantine (MEM) or placebo will be given and titrated from 5 mg/day to 10mg/twice a day (or 20mg a day) over the course of the first four weeks. Subjects will be instructed to take one tablet of escitalopram a day in the evening or in the morning, as preferred; and 1 pill of MEM (in 5 mg increments) or placebo at 8 am for the first week, and at 8 am and 3 pm in the second week and thereafter. The dose of MEM will be increased every 7 days: second week 5 mg (1 pill) twice a day; third week 5 mg (1 pill) at eight o'clock in the morning and 10 mg (2 pills) at three o'clock in the afternoon; fourth week 10 mg (2 pills) at eight o'clock in the morning and three o'clock in the afternoon. At the end of week 4, patients with a CGI improvement rating of 3 or greater will be titrated upward on the
 	
 
		Describe the approved indications for the use of the drug/biologic and how the drug/biologic will be used in the study:	
Approved indications and usage: Namenda (memantine hydrochloride) is indicated for the treatment of moderate to severe dementia of the Alzheimer's type. Patients who meet all eligibility criteria at baseline will be given a 14-day supply of the study medications prepared and dispensed by the UCLA Pharmacy in the matching capsules. All subjects will receive 10-20mg of escitalopram open-label throughout the trial. Matching capsules containing memantine (MEM) or placebo will be given and titrated from 5 mg/day to 10mg/twice a day (or 20mg a day) over the course of the first four weeks. Subjects will be instructed to take one tablet of escitalopram a day in the evening or in the morning, as preferred; and 1 pill of MEM (in 5 mg increments) or placebo at 8 am for the first week, and at 8 am and 3 pm in the second week and thereafter. The dose of MEM will be increased every 7 days: second week 5 mg (1 pill) twice a day; third week 5 mg (1 pill) at eight o'clock in the morning and 10 mg (2 pills) at three o'clock in the afternoon; fourth week 10 mg (2 pills) at eight o'clock in the morning and three o'clock in the afternoon. At the end of week 4, patients with a CGI improvement rating of 3 or greater will be titrated upward on the
		
Describe the approved indications for the use of the drug/biologic and how the drug/biologic will be used in the study:	
Approved indications and usage: Namenda (memantine hydrochloride) is indicated for the treatment of moderate to severe dementia of the Alzheimer's type. Patients who meet all eligibility criteria at baseline will be given a 14-day supply of the study medications prepared and dispensed by the UCLA Pharmacy in the matching capsules. All subjects will receive 10-20mg of escitalopram open-label throughout the trial. Matching capsules containing memantine (MEM) or placebo will be given and titrated from 5 mg/day to 10mg/twice a day (or 20mg a day) over the course of the first four weeks. Subjects will be instructed to take one tablet of escitalopram a day in the evening or in the morning, as preferred; and 1 pill of MEM (in 5 mg increments) or placebo at 8 am for the first week, and at 8 am and 3 pm in the second week and thereafter. The dose of MEM will be increased every 7 days: second week 5 mg (1 pill) twice a day; third week 5 mg (1 pill) at eight o'clock in the morning and 10 mg (2 pills) at three o'clock in the afternoon; fourth week 10 mg (2 pills) at eight o'clock in the morning and three o'clock in the afternoon. At the end of week 4, patients with a CGI improvement rating of 3 or greater will be titrated upward on the
					

Generic name of the drug/biologic

Investigational Drug/Biologics Information

escitalopram dose and instructed to take two tablets, or 20 mg /day. Patients with a CGI improvement rating of 1 or 2 will continue taking the same dose they have been taking at the end of week 3. If patients experience any side-effects attributed to their study medication use, the allowed dose adjustment for MEM will be decreasing MEM by 1– 3 pills, to a minimum of 5mg (or 1 cap a day), and decreasing escitalopram dose to 10 mg, so that the allowed dose range of escitalopram will be 10-20mg/day. Re-challenge with a higher dose of MEM up to 20mg/ day, or escitalopram of up to 20mg/day may take place at the following visit in case of an incomplete response. All dose adjustments will be documented and considered in the analyses. The expected effective dose range of MEM will be 20mg daily, which has been successfully used and well-tolerated in our pilot study. At the end of 24 weeks, memantine and placebo will be tapered off gradually in the same decrement of 5mg (or 1 pill) per week over the course of 2-4 weeks to reduce the risk of withdrawal symptoms. At 6 months, subjects who decide to discontinue escitalopram will be tapered off gradually over the course of 2-4 weeks with 5mg dose decrements/ week in cooperation with their psychiatrist.

The new use is not intended to be reported to the FDA:

Yes

The new use is not intended to support a significant change in advertising for the drug/biologic:

Yes

The new use does not involve a change in the route of administration, dosage level, subject population or other factor that significantly increase the risks:

Yes

The new use does not intend to invoke a waiver of informed consent

Yes

Generic name of the drug/biologic

Investigational Drug/Biologics Information

	for emergency research:	
	If you answered "false" to any of the items above and believe that an IND is not needed, provide a justification:	No Value Entered
Use of an Unapproved Drug or Biologic, or if use of this drug or biologic requires an IND:		
Identify all persons who will prescribe the drug or biologic:	The study doctor and PI, [name]. will prescribe the drug.	
The route of administration:		
"Other" route, specify:	No Value Entered	
The location(s) where the drug/biologic will be administered:	 	
If you indicated that administration will take place in an inpatient unit, or at a non-UCLA site, specify the location and where in the location the medication will be administered:	No Value Entered	

3.0 All drugs and biologics for research at UCLA are to be managed through the UCLA Pharmacy. Provide your assurance that you have or will submit an Investigational Drug Study application to the Pharmacy.

Agree

ID: IRB#12-001714

View: NEW 8.7 - Genetic Analyses/Genotyping

This view has been locked by amendment(s)

Warning: Save your work at least every 15 minutes by clicking "Save" or "Continue."

Genetic Analyses/Genotyping

You indicated that this study includes genetic analyses/genotyping (section 2.3/item 1.0). Please provide the following information.

1.0 *Are you performing whole genome sequencing?

Yes No

2.0 *Are you planning to provide study participants with the results of the genetic analyses/genotyping?

Yes No

If you answered "yes", answer the next set of items below. If you answered "no", continue to the next screen.

3.0 List the types of tests:

4.0 Is the genotyping being performed by a Clinical Laboratory Improvement Amendments (CLIA) approved lab?
 Yes No

5.0 Describe the rationale for providing study participants with the results of the genetic tests/genotyping; explain what, how, and by whom the participants and/or their healthcare provider will be told about the meaning, reliability and applicability of the results and how the information will be provided (e.g., in person, by letter).

6.0 Indicate the qualifications of the person who will relay the information.

A licensed study physician

A licensed genetic counselor

Other

6.1 If "other", specify.

ID: IRB#12-001714

View: NEW 8.11 - Radiation

This view has been locked by amendment(s)

Warning: Save your work at least every 15 minutes by clicking "Save" or "Continue."

Radiation (read-only historical information)

NOTE: This section includes read-only historical information for studies that included radiation procedures prior to the September 2018 transition from webIRB to SafetyNet for describing radiological procedures. The contents of this section are superseded by any related SafetyNet application and should not be considered part of the approved application.

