The proposed project will also evaluate the role of neuroimaging biomarkers of brain aging (i.e., neurodegenerative and vascular brain changes) and mild cognitive impairment in the patterns of treatment response to memantine combined with escitalopram compared to escitalopram and placebo. Memantine is likely to accelerate and enhance antidepressant response to escitalopram and improve cognitive performance. Subjects with amnesic mild cognitive impairment or biomarkers of brain aging at baseline are likely to have preferential response to the combination of memantine and escitalopram compared to escitalopram and placebo.

We will conduct neuroimaging using two functional and structural magnetic resonance imaging (MRI) scans and a positron emission tomography (PET) scan. The purpose of the imaging procedure is to measure the amyloid and tau protein in the brain using the identified substance called [18F]FDDNP to predict the response to depression and memory treatments.

Additionally, we will explore the levels of telomerase and NFkappaB as correlates of depression as predictors of response to the interventions directed toward improvement in the severity of depression, quality of life and resilience. We will examine the role of 2 candidate genes involved in the regulation of mood and memory, and evaluate telomerase and NFkappaB activity before and after the intervention. This proposal is a continuation of our ongoing work in this area.

2.0 ***List three to five keywords describing this study (separate the words with commas). The keywords may be used for identifying certain types of studies.**

geriatric depression, MCI, neuroimaging, biomarkers, memantine

3.0 *** Is this study conducted or supported by HHS (e.g., the National Institutes of Health, Centers for Control and Prevention, etc.)?**

Yes No

3.1 *** Is NIH the HHS agency supporting or conducting the study?**

Yes No

3.2 *** Please choose one:**

I acknowledge that my study is automatically covered by a Certificate of Confidentiality and I understand the responsibilities associated with that Certificate.

The NIH Certificate of Confidentiality policy does not apply to my study (see guidance at right and explain below)

4.0 *** Is this study regulated by the Food and Drug Administration (FDA)?**

Yes No

4.1 **If yes, check all that apply:**

Human Drugs

Medical Devices

Biological Products

Mobile Medical Applications

Food Additives

Color Additives

Other

ID: IRB#12-001714

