Specific Aim 1. To compare the quality of treatment response in older depressed subjects to escitalopram+placebo (esCIT+PBO) vs. escitalopram+memantine (esCIT+MEM) in a 6 month acute treatment trial with 12 month follow up.

Hypothesis 1. Improved levels of depression and cognition will be observed in depressed subjects treated with combined escitalopram+memantine compared to those treated with escitalopram+placebo.

Specific Aim 2. To determine the role of a) brain pathology (MRI and FDDNP-PET measures) and b) MCI diagnosis in predicting and moderating antidepressant response to study drugs in depressed subjects.

Hypothesis 2a. Measures of brain pathology (volume and localization of white matter hyperintensities, regional gray and white matter volumes, hippocampal atrophy, functional brain connectivity using cognitive task activation, FDDNP-PET binding levels) will predict and moderate antidepressant response to escitalopram and memantine or escitalopram and placebo in: 1) rate of remission; 2) rate of depression relapse; and 3) improvement in cognitive performance.

Hypothesis 2b. MCI diagnosis will predict and moderate preferential antidepressant response to escitalopram and memantine.

Aim 3: To test whether the two treatment conditions can improve neurocognitive performance and working memory function surveyed with task-related fMRI at 12 weeks and/or during the 6 months follow-up. Hypothesis 3a: Compared to escitalopram+PBO, escitalopram+MEM will improve cognitive performance on tests of a) memory after 12week treatment and at 6 months follow-up. Hypothesis3b: Likewise, escitalopram+MEM will increase working memory-related activation of dorso-lateral prefrontal cortex (DLPFC)

Aim 4. To determine whether both structural and functional brain imaging markers will predict and/or moderate antidepressant response in both treatment conditions.

Hypothesis 4: Imaging biomarkers will moderate and predict 1) rate of remission; 2) rate of depression relapse and recurrence; and 3) improvement in cognitive performance.

Exploratory hypothesis 1: We will explore the relationship of apolipoprotein E-4 allele (APOE-4) to [18F]FDDNP PET binding in subjects with DEP+MCI. We expect that APOE-4 allele carriers will have higher FDDNP binding in the medial temporal lobe compared to non-carriers, and will experience greater cognitive decline on neuropsychological tests and fMRI memory tests.

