Data Analysis. Primary analyses will be carried out on an intent-to-treat basis; additional analyses considering dropout or other observable post-randomization outcomes will make use of an instrumental-variable analysis framework. Data will be examined initially to identify issues such as departures from normality, which would suggest the need for transformations (e.g., logarithmic) and influential observations (outliers). Descriptive statistics will be computed and reported overall and by group. Demographic variables and variables characterizing the course of depression (e.g., age of onset, chronicity, number of episodes) will be screened to determine which have relationships with the outcome variables that would suggest their value as covariates. Variables that demonstrate meaningful associations with outcomes controlling for treatment group and are substantially different across groups are candidates for covariates. Demographic variables, baseline depression, and other potential covariates will be compared between the two groups to help determine if the randomization was successful in making the two groups comparable. Specific analysis plan follows below.

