Hypothesis 1. The primary outcome, namely responder/remitter status, will be compared between the esCIT+MEM and esCIT+PBO groups using chi-square statistics. Days to remission will be analyzed using the Kaplan-Meier survival method with treatment group as a stratification variable using the day on which response was observed as the event indicator. The survival function estimates the proportions achieving the response criterion, while the overall survival curve reflects speed of response. The independent variable is treatment group with two levels. A log-rank test will be used to assess the significance of any difference between treatment arms, and Cox regression to reflect the role of baseline covariates. We will also report the total time spent below the response threshold, compare summary statistics, and patterns of response within the patient over time. Analysis of change over time will be performed using linear mixed model analysis of covariance (SAS PROC MIXED). The linear mixed model permits flexible specification of the covariance structure of the repeated measures within patient, and allows analysis of incomplete cases using maximum likelihood. The outcome measures will be the HAM-D scores as well as cognitive domain scores (i.e. memory, processing speed, executive function) with the baseline rating/score on each domain as a covariate.

Hypothesis 2a. The role of brain neuroimaging biomarkers in variability of treatment response is examined in this Hypothesis. Predictor variables: We predict that baseline measures of neuroimaging biomarkers (white matter hyperintensity, regional gray or white matter volumes, hippocampal thickness and regional FDDNP binding levels) will be related to treatment outcomes. These predictions will be evaluated in the context of the models described above (i.e., general linear mixed model) by adding the posited prognostic variable as an additional predictor. Moderator variables: A limited number of exploratory analyses will be performed to evaluate possible moderators of each treatment strategy. Statistical evaluation of moderators will be done by including the posited moderator variable as an independent variable and evaluating the moderator x treatment group interaction term. Mediator Variables: We will evaluate the variable as a potential

mediator using a principal stratification framework.17,20

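### Age at entry is not pre-specified in the imaging predictor models, nor age x treatment in the exploratory moderator models, so a marker that only tracks age could be read as brain pathology predicting or moderating response

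*Combined protocol and SAP*

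**What the plan says.** **Hypotheses** (View NEW 10.1, item 2.0). Hypothesis 2a states that measures of brain pathology "will predict and moderate antidepressant response to escitalopram and memantine or escitalopram and placebo". Hypothesis 4 says much the same of imaging biomarkers generally. The lay summary (View NEW 2.2) presents the aim as to "evaluate the role of neuroimaging biomarkers of brain aging (i.e., neurodegenerative and vascular brain changes").

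**Predictor models** (item 6.0, Hypothesis 2a). Each marker is tested in the Hypothesis 1 mixed model "by adding the posited prognostic variable as an additional predictor". That model is specified "with the baseline rating/score on each domain as a covariate"; no other covariate is named.

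**Moderator models** (same paragraph). Moderators are tested by "including the posited moderator variable as an independent variable and evaluating the moderator x treatment group interaction term". These are labelled exploratory: "A limited number of exploratory analyses will be performed to evaluate possible moderators of each treatment strategy".

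**MRI regressions** (item 4.0, Integration with Mood and Neurocognitive Measures). A separate general linear model is fitted for each MRI method. Significant markers then go forward to a stepwise regression. Age is not named at either stage.

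**Covariate selection** (item 6.0, Data Analysis). Demographic variables "will be screened to determine which have relationships with the outcome variables that would suggest their value as covariates". The plan continues: "Variables that demonstrate meaningful associations with outcomes controlling for treatment group and are substantially different across groups are candidates for covariates".

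**Stratification** (item 4.0) is by a-MCI status and by age at onset of depression, not by current age.

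**The concern.** The candidate rule is built for the randomised contrast: it asks whether a variable is related to outcome and also differs between arms. A marker contrast is not randomised. If older patients have more white matter hyperintensity, smaller volumes or higher FDDNP binding, and older patients also respond differently, marker and outcome are associated across the whole sample however well age is balanced between arms. By the plan's own description these are markers of brain ageing, so some relation to age is to be expected.

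Interpretation is what is at stake. The Innovation text in item 3.0 looks ahead, if the hypotheses hold, to treatment choices tailored by atrophy, white matter hyperintensity and FDDNP binding. If age is not in the model, a significant marker cannot be separated from date of birth, which needs no scan. For moderators, marker x treatment can likewise pick up an age x treatment effect.

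**Working it through.** **The plan's own figure.** Item 6.0 gives no power and no correlations for the marker tests, only power above 80% for the primary chi-square comparison. The sample size used below comes from that calculation: 134 x 0.75 = 100.5, about 50 completers per arm. With 70% versus 40% remission, power = Phi[(0.30 - 1.96 x sqrt(2 x 0.55 x 0.45 / 50)) / sqrt((0.21 + 0.24) / 50)] = Phi[(0.30 - 0.195) / 0.0949] = Phi(1.107) = 0.866. The stated figure is reproduced.

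**Step 1: how often would chance imbalance bring age in?** The standard error of a standardised difference is sqrt(2/n per arm). The plan does not define a substantial difference, so the cut-offs are assumptions.

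| Per arm | SE | P(difference > 0.25 SD) | P(difference > 0.4 SD) |
|---|---|---|---|
| 50 | 0.200 | 21% | 4.6% |
| 67 | 0.173 | 15% | 2.1% |

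Age must also be associated with the outcome, so the chance that it qualifies is lower still.

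**Step 2: a marker with no effect of its own.** Assume marker-age correlation a and age-outcome correlation b. Within arms the marker-outcome correlation is then r = a x b. With n = 100, z is about r / sqrt(1 - r^2) x sqrt(97), and the rejection rate is about Phi(z - 1.96) + Phi(-z - 1.96).

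- a = 0.3, b = 0.1: r = 0.03, z = 0.296, rate = 0.048 + 0.012 = 6.0%
- a = 0.3, b = 0.2: r = 0.06, z = 0.592, rate = 0.086 + 0.005 = 9.1%
- a = 0.5, b = 0.3: r = 0.15, z = 1.494, rate = 0.321 + 0.000 = 32%

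A simulation with 4,000 runs per setting (linear model, nominal 5%) agrees and adds the effect of each possible rule for age:

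| a, b | Age never in | Rule: outcome p < 0.05 and difference > 0.25 SD | Trials in which that rule admits age | Rule: outcome p < 0.05 only | Age always in |
|---|---|---|---|---|---|
| 0.3, 0.1 | 6.1% | 6.0% | 3% | 5.2% | 5.3% |
| 0.3, 0.2 | 9.1% | 8.4% | 11% | 5.1% | 5.3% |
| 0.5, 0.3 | 31.9% | 26.4% | 17% | 5.3% | 5.0% |

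The two-part rule removes little of the excess. A rule based on outcome association alone would remove nearly all of it.

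**Step 3: moderators.** Suppose age is the true moderator and the marker merely tracks it. The assumed shift in treatment effect is 0.3 to 0.5 SD per SD of age (n = 100).

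| Marker-age, shift | No age term | Age main effect only | Age and age x treatment |
|---|---|---|---|
| 0.3, 0.3 | 7.4% | 7.5% | 5.1% |
| 0.5, 0.3 | 10.9% | 11.0% | 4.6% |
| 0.5, 0.5 | 21.9% | 21.6% | 5.0% |
| 0.7, 0.5 | 38.0% | 37.9% | 4.8% |

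Age as a main effect does not help here; the interaction term is needed.

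**The case against.** **A reader might infer that the plan excludes age.** It does not. The screening sentence rests on relation to outcome alone and covers demographic variables. The next sentence describes candidates without saying that nothing else may enter. The Cox model under Hypothesis 1 refers to baseline covariates without listing them, and the white matter paragraph in item 4.0 allows for control of linked clinical measures and vascular risk factors. If age were admitted on outcome association alone, the predictor problem would all but vanish, as Step 2 shows. This stands: the text is ambiguous. But the only stated definition of a candidate joins the two conditions, and none of these places supplies age x treatment.

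**A reader might call any unadjusted finding a false positive.** That goes too far. A marker that tracks age does predict response in the plain prognostic sense, and ageing may act through the pathology measured, so adjustment can remove real signal. What the unadjusted model cannot support is a claim about pathology as distinct from age, or about value beyond age.

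**The size is assumed.** This stands. The simulation is a linear model without the baseline score, whereas the plan adjusts for it, so only the age-outcome association beyond baseline counts. Remission is binary. A moderator shift of 0.3 to 0.5 SD is 39% to 66% of the pilot's 0.76 SD effect (0.3/0.76, 0.5/0.76), and nothing in the documents supports an age interaction that large. Fewer than 100 may be scanned, since MRI-ineligible patients receive CT and PET consent is a separate checkbox.

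**Moderator results might be read as confirmatory.** Item 6.0 labels them exploratory, although item 2.0 words moderation as a hypothesis. The predictor tests carry no such label. Item 6.0 sets out no separate model for Hypothesis 4.

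The attached grant proposal listed in item 1.0 is not among the documents reviewed and may hold further imaging detail.

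**Conclusion.** The point holds in a limited form. Age at entry is not pre-specified in the Hypothesis 2a predictor models or in the MRI linear models and stepwise regression, and age x treatment is not pre-specified in the exploratory moderator models. The stated candidate rule would normally admit age only through chance imbalance between arms, a condition that has no bearing on a non-randomised marker contrast.

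The consequence ranges from negligible to material: about 6%, 9% or 32% at n = 100 under the three assumed pairs of correlations, against about 5% with age included. These rates illustrate the mechanism; they do not estimate what will happen in this trial. They rest on correlations that the documents do not give and on a model without the baseline-score adjustment. The randomised comparison of memantine with placebo is untouched.

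**What to change.** 1. In item 6.0 (Hypothesis 2a) and item 4.0 (MRI linear models and final stepwise regression), include age at entry as a fixed covariate in every imaging predictor model, whatever the balance between arms. In the stepwise model, force age in.
2. In the moderator models, add age and age x treatment beside marker and marker x treatment.
3. Report each marker result with and without age. Word any claim that pathology predicts or moderates response, or that a scan adds to what age already tells, from the age-adjusted result.
4. In item 6.0 (Data Analysis), state that the arm-imbalance rule applies to the treatment comparison and does not govern the imaging models.

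The cost is a change of wording and one or two degrees of freedom per model; no new data are needed. Intervals will be somewhat wider for markers strongly related to age, and adjustment may remove signal where ageing acts through the marker, which is why both results are reported.
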